175 combination therapy (excluding GLP1 receptor agonists) or on low-dose insulin therapy
176 (TDD ≤ 0.4 unit/kg/day) prior to admission.
- 177 4. Subjects with a hospital admission BG < 400 mg/dL without laboratory evidence of diabetic
178 ketoacidosis (serum bicarbonate < 18 mEq/L or positive serum or urinary ketones).
- 179 5. BMI > 25 Kg/m² and ≤ 45 Kg/m²

181 **Exclusion Criteria**

- 182 1. Age < 18 or > 80 years.
- 183 2. Subjects with stress hyperglycemia (BG > 140 mg/dL and HbA1c < 6.5%)
- 184 3. Subjects with a history of type 1 diabetes (1).
- 185 4. Treatment with GLP1 analogs during the past 3 months prior to admission.
- 186 5. Recurrent severe hypoglycemia or hypoglycemic unawareness.
- 187 6. Subjects with gastrointestinal obstruction, gastroparesis or those expected to require
188 gastrointestinal suction.
- 189 7. History of medullary thyroid cancer or multiple endocrine neoplasias
- 190 8. Patients with acute or chronic pancreatitis, pancreatic cancer or gallbladder disease.
- 191 9. Patients with clinically significant hepatic disease (cirrhosis, jaundice, end-stage liver
192 disease, portal hypertension) and elevated ALT and AST > 3 times upper limit of normal, or
193 significantly impaired renal function (GFR < 30 ml/min).

- 194 10. Treatment with oral or injectable corticosteroid (equivalent or higher than prednisone
195 5mg/day), parenteral nutrition and immunosuppressive treatment.
196 11. Mental condition rendering the subject unable to understand the nature, scope, and possible
197 consequences of the study.
198 12. Female subjects who are pregnant or breast-feeding at time of enrollment into the study.
199 13. Females of childbearing potential who are not using adequate contraceptive methods (as
200 required by local law or practice).

201

202 **Investigational drugs.**

203

- 204 • Liraglutide 6.0 mg/mL solution for subcutaneous (s.c.) injection. The solution will be
205 provided in 3 mL prefilled pen.
- 206 • Liraglutide will be provided to patients
- 207 • Glargine will be provided

208

209

210 **Withdrawal Criteria**

211

- 211 1. The subject may withdraw at will at any time.
- 212 2. The subject may be withdrawn from the trial at the discretion of the investigator due to a
213 safety concern or if judged non-compliant with trial procedures or included in contravention
214 to the inclusion and/or exclusion criteria.
- 215 3. Subject diagnosed with acute pancreatitis by clinical and/or radiographic criteria.

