Gastrointestinal side effects including nausea and vomiting are more common in patients treated with liraglutide compared to placebo. The frequency of nausea and vomiting is reported in up to 14% of patients receiving higher doses of liraglutide 1.8 mg in combination to metformin and sulfonylurea therapy compared to 3.5% in patients receiving placebo plus OADs (Victoza package insert). The number of adverse events will be collected at each telephone contact or clinic visit. There have been few reported events of acute pancreatitis. Subjects should be informed of the characteristic symptoms of acute pancreatitis: persistent, severe abdominal pain. If pancreatitis is suspected, liraglutide and other potentially suspect medicinal products should be discontinued. If the investigator suspects acute pancreatitis, all suspected drugs should be discontinued until confirmatory test have been conducted and appropriate treatment should be initiated. Subjects diagnosed with acute pancreatitis (as a minimum 2 of 3: characteristic abdominal pain, amylase and/or lipase >3xUNR or characteristic findings on CT scan/ MRI should be withdrawn from the study.

Protection against Risks:

We will follow safeguards to minimize the risk to our subjects: a) we will carefully monitor response to medical treatment every 2 weeks by telephone contact and every 3 months during clinic visits, b) women of reproductive age who are sexually active will undergo a urine pregnancy tests prior to participation in the study, c) female subjects whom are pregnant, breast-feeding, or not willing to use appropriate contraception at time of enrollment will not be included in the study, d) patients with significant comorbidities such as chronic kidney disease

420 greater than stage III, liver cirrhosis, gastroparesis, and pancreatic disorders will be excluded
421 from the study.

422
423 Hypoglycemia: Patients will receive diabetes education prior to discharge and will be instructed
424 on hypoglycemia sign/symptoms and treatment. Patients will be asked to call the diabetes center
425 and/or PCP in the event of hypoglycemia. If a patient develops hypoglycemia, the dose of OAD
426 will be reduced or discontinued and the daily dose of basal insulin will be reduced by 10% to
427 30% (see treatment algorithm).

428 Gastrointestinal side effects including nausea and vomiting may be expected, more commonly in

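### Read literally, exclusion 9 does not exclude cirrhosis unless ALT and AST are also raised, while the safety section excludes cirrhosis with no enzyme condition

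*Combined protocol and SAP*

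**What the plan says.** Exclusion Criteria, item 9, is a single sentence running over three lines. It opens with "Patients with clinically significant hepatic disease (cirrhosis, jaundice, end-stage liver", continues "disease, portal hypertension) and elevated ALT and AST > 3 times upper limit of normal, or", and ends with "significantly impaired renal function (GFR < 30 ml/min".

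The Protection against Risks section, which sets out safeguards for participants, covers the same ground in its point d): "included in the study, d) patients with significant comorbidities such as chronic kidney disease" "greater than stage III, liver cirrhosis, gastroparesis, and pancreatic disorders will be excluded". Cirrhosis is named there without any laboratory condition.

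No other inclusion or exclusion item refers to cirrhosis or to liver disease of any kind. The Informed Consent section says that research staff enrol patients by applying the inclusion and exclusion criteria set out elsewhere in the protocol.

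**The concern.** Item 9 uses two different connectives. The liver diagnoses are tied to the enzyme threshold by *and*; the renal condition is set apart by *or*. A reader who takes these words at face value concludes that the hepatic exclusion needs a diagnosis and raised enzymes together. A reader of Protection against Risks concludes that a diagnosis of cirrhosis is enough.

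Two things are at stake. The first is a protective rule: the protocol presents the exclusion of cirrhosis as a safeguard, and the criterion that should put it into effect may not do so. The second is consistency. This is a multi-center trial in which, under Randomization and Blinding, a member of the local team runs randomization and group assignment at each institution, and the documents describe no central check of eligibility. Sites that read item 9 differently would make different decisions about the same kind of patient.

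**Working it through.** There is no figure to reproduce. The check is whether the two sections give the same decision for the same patient.

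**Inputs.** Let H be clinically significant hepatic disease (cirrhosis makes H true), E be ALT and AST both above 3 times the upper limit of normal, and R be GFR below 30 ml/min. All three come from item 9. The safety rule, cirrhosis excluded, comes from Protection against Risks.

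**Readings of item 9.**
- Literal: excluded if (H and E) or R.
- List: excluded if H or E or R.

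**Patient with cirrhosis (H true), all four combinations of E and R.**

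| E | R | Item 9, literal | Item 9, list | Protection against Risks |
|---|---|---|---|---|
| yes | no | excluded | excluded | excluded |
| yes | yes | excluded | excluded | excluded |
| no | yes | excluded | excluded | excluded |
| no | no | **not excluded** | excluded | excluded |

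The sections disagree in one row of the four: cirrhosis, enzymes not both above the threshold, GFR at least 30 ml/min. The disagreement arises only on the literal reading.

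**Second ambiguity.** The enzyme condition names ALT *and* AST. Taken literally, both must exceed the threshold. If either one were enough, a patient with cirrhosis, GFR at least 30 ml/min and only one raised enzyme would move from not excluded to excluded under the literal reading. Item 9 does not say whether one enzyme is enough.

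**Which reading does the list itself support?** The evidence is mixed.
- Within item 9, the change to *or* before the renal limb favours the literal reading.
- Items 6, 7 and 8 also use *or* when they list alternatives, which points the same way.
- Item 2 uses *and* in the strict sense, for two laboratory conditions that must both hold.
- Item 10 uses it loosely: "5mg/day), parenteral nutrition and immunosuppressive treatment" closes a list that can hardly be meant to exclude only patients receiving everything in it.

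**Comparison with the other named conditions.** The other conditions named in point d) have counterparts in the numbered list: gastroparesis in item 6, pancreatic disorders in item 8, and kidney disease in the renal limb of item 9. Each of those stands alone there. Cirrhosis is the only one whose counterpart can be read as carrying an extra condition.

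**The case against.** The strongest reply is that a protocol is read as a whole. Protection against Risks says that cirrhosis is excluded, item 10 shows that *and* is used loosely in this list, and the sensible reading of item 9 is therefore a list of separate conditions. On that reading nothing conflicts.

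Part of this stands. The list reading is available, so a reader who infers that the protocol makes patients with cirrhosis eligible goes too far. The documents support only that item 9, read literally, does not exclude them in one combination of findings, and such a patient must still meet every other criterion. But the reply depends on correcting item 9 from another section. The *or* inside item 9 works against that correction, and staff are told to enrol from the criteria.

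Three further inferences are tempting and are not supported.
- *A count of affected patients.* Study Schedule gives about 2000 screened and 280 randomized (280/2000 = 14%). The documents give no frequency of liver disease, and a rate applied to everyone screened would include patients who are not enrolled for other reasons.
- *Extra loss after randomization through withdrawal criterion 2.* That criterion covers subjects enrolled in contravention of the eligibility criteria. On the literal reading the patient with cirrhosis does not breach item 9; on the list reading item 9 excludes the patient and the gap disappears. The argument cannot use both readings.
- *A need for raised enzymes alone to exclude a patient.* Protection against Risks does not mention transaminases, so there is no contradiction on that point to resolve.

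**Conclusion.** The point holds as an ambiguity in a protective eligibility rule that, on its literal reading, conflicts with the protocol's own safety section. The conflict is confined to patients with cirrhosis whose ALT and AST are not both above the threshold and whose GFR is at least 30 ml/min.

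The conclusion rests on two things that can be checked in the text: the connectives in item 9, and the absence of any other liver criterion. It does not depend on an assumed prevalence. The number of patients affected cannot be derived from the documents. No estimate, test, power or sample-size figure changes.

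It is more than a slip of wording, because staff following item 9 as written could reach a decision that the safety section rules out. It should be corrected, since doing so costs almost nothing. Which section states the intended clinical rule cannot be settled from the documents and is for the sponsor to decide.

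**What to change.** Reconcile item 9 of the Exclusion Criteria with Protection against Risks so that both give the same eligibility decision for a patient with cirrhosis. In doing so:

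1. Write the connectives between the hepatic, enzyme and renal conditions explicitly, so that it is clear which stand alone and which must occur together.
2. State whether one or both of ALT and AST must exceed the threshold.
3. Use matching wording in both sections.

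The cost is a change to one criterion and, if needed, to one sentence in the safety section; no new assessment is required. If the sections are reconciled towards Protection against Risks, a few more screened patients will be excluded. If they are reconciled towards the literal item 9, the safety section must be amended so that it no longer states an unconditional exclusion of cirrhosis.

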96 to liraglutide or glargine with or without oral agents at hospital discharge.
97

98 **Endpoints:**

99 **Study Outcomes:**

100 The primary outcome of the study is to determine differences in HbA1c concentration at 26
101 weeks from discharge between liraglutide and glargine insulin therapy.
102

103 The secondary outcome is to compare differences between treatment groups in any of the
104 following measures during the 26 weeks following hospital discharge in patients with T2D:

- 105 • Self-measured blood glucose (SMBG) 7-point profiles
- 106 • Fasting and postprandial BG concentration
- 107 • Incidence rate and number of hypoglycemic events (<70 mg/dl) and severe hypoglycemic
108 events (<40 mg/dl).
- 109 • Percent of patients with 26 week HbA1c $<7.0\%$ and no hypoglycemia
- 110 • Percent of patients with 26 week HbA1c $<7.0\%$ and no weight gain
- 111 • Percent of patients with 12 week HbA1c $<7.0\%$ and no hypoglycemia
- 112 • Change in body weight and BMI

- 113 • Cardiovascular risk factors including changes in blood pressure, heart rate, and lipid
- 114 profile.
- 115 • Total daily dose of insulin
- 116 • Number of emergency room visits and hospital readmissions
- 117 • Acute renal failure during the 26-week follow-up defined as a clinical diagnosis of acute
- 118 renal failure with documented new-onset abnormal renal function (increment in
- 119 creatinine ≥ 0.5 mg/dL from baseline)

120
121

122 **Study type:**

123 The trial is a 26-week, randomized, open label-controlled two-armed, multi-center, multi-
124 national trial investigating the efficacy and safety of liraglutide versus glargine insulin in
125 medicine and surgical patients with T2D after hospital discharge.

126 We will recruit a total of 330 poorly controlled (HbA1c $\geq 7\%$ -10%) patients with T2D treated
127 with diet or oral antidiabetic agents (OAD) or on low-dose insulin therapy (TDD ≤ 0.4
128 unit/kg/day) prior to admission. Patients will be treated with a standard basal bolus insulin
129 regimen during the hospital stay. Prior to hospital discharge, patients will be randomized to
130 liraglutide or glargine with or without oral antidiabetic drugs. After discharge, a member of the
131 diabetes research team will contact patients via telephone call every 2 weeks to assess response
132 to therapy. In addition, patients will be asked to attend an outpatient clinic visit at 2 (optional), 4,

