133 12 and 26 weeks after hospital discharge. Recommendation on insulin dose adjustment will be
134 provided to patients at each telephone contact and clinic visits.

135
136 Recommendation for liraglutide dose escalation will be done every one or two weeks until the
137 maintenance dose of 1.8 mg is reached. Dose escalation can be extended over 2 weeks at the
138 discretion of the investigator in case of gastrointestinal adverse events. Liraglutide and insulin
139 will be add-on to the subject's pre-admission OAD regimen. Dose of OAD should remain
140 unchanged throughout the trial, however dose reduction of insulin and sulfonylurea is allowed
141 due to hypoglycemia.

142
143
144 **Study Groups:**

145 We plan to analyze a total of 280 patients (who receive study medication) with T2D at the time
146 of hospital discharge.

- 147
- 148 • Group 1. Liraglutide once daily in combination to OADs (n=140).
- 149
- 150 ▪ Group 2. Glargine once daily in combination to OADs (n=140).

151
152

153 **Study population:**

154 This will analyze 380 general medicine and surgical patients with a known history of T2D, age
155 18-80, treated with diet alone and/or oral antidiabetic agents including sulfonylureas, repaglinide,
156 nateglinide, DPP4s, SGLT2, or metformin as monotherapy or in combination therapy or on low-
157 dose insulin therapy (TDD ≤ 0.4 unit/kg/day) prior to admission. Subjects will be recruited from 5
158 medical centers in the United States. A total of 300 patients will be recruited at Grady Memorial
159 Hospital, Emory University Hospital and Emory Midtown hospital.

161 **Study Sites:** This study will be performed at Grady Memorial Hospital, Emory University
162 Hospital, Emory University Hospital at Midtown, and 3 institutions in the United States:

- 163 1. MetroHealth Medical Center, Cleveland (PI: [name].)
- 164 2. State University of NY at Buffalo (PI: [name].)
- 165 3. University of Miami, Florida (PI: [name].)
- 166 4. Sanatorio Guemes, Buenos Aires -Argentina (PI: [name])

169 **Inclusion Criteria**

- 170 1. Males or females between the ages of 18 and 80 years discharged after hospital admission
171 from non- ICU general medicine and surgical services (excluding gastrointestinal and
172 cardiac surgeries).
- 173 2. Admission HbA1c between 7% and 10%
- 174 3. Patients with T2D treated with diet alone or with oral antidiabetic agents as monotherapy or in

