- 216 4. If the fasting BG and average daily BG on 3 consecutive days exceeds > 15.0 mmol/L (240
217 mg/dL). If this occurs, the subject will be called for an unscheduled visit as soon as possible.
218 A confirmatory FPG should be obtained and analyzed by the hospital laboratory. If this FPG
219 exceeds 15.0 mmol/L (240 mg/dL), and no treatable intercurrent cause for the hyperglycemia
220 has been identified, the subject must be withdrawn.
- 221 5. Pregnancy or intention to become pregnant.

222 **Subject Replacement**

223 There will be no replacement of subjects in this trial.

224

225 **Rationale for Study Population**

226 We will recruit patients with poorly controlled T2D (HbA1c \geq 7%-10%) treated with diet and/or
227 oral antidiabetic agents or on low-dose insulin therapy (TDD \leq 0.4unit/kg/day)prior to admission.
228 Patients will be treated with a basal bolus insulin regimen during the hospital stay (standard of
229 care). Prior to hospital discharge, patients will be randomized to receive liraglutide or glargine
230 as monotherapy in treatment of patients treated with low-dose insulin therapy (TDD \leq 0.4
231 unit/kg/day) (or as add-on therapy to the subject's pre-admission OAD regimen.

232

233 We plan to analyze a total of 280 patients (who receive study medication) with T2D at the time
234 of hospital discharge [liraglutide once daily in combination to OADs (n=140) or glargine once
235 daily in combination to OADs (n=140)].
236

237 **GROUP 1. Liraglutide Treatment Group.**

238

239 **▪ Patients receiving no Therapy prior to admission:**

- 240 • Discharge on liraglutide once daily.
 - 241 • Start metformin if A1C \geq 8% and no contraindications.
- 242

243 **▪ Patients receiving OAD prior to admission:**

- 244 • If no contraindication, restart pre-admission OADs according to standard of care and
245 investigator's medical discretion (metformin, sulfonylureas, nateglinide, repaglinide,
246 pioglitazone) in combination to liraglutide.
 - 247 • The total daily dose of insulin secretagogues (sulfonylureas, nateglinides and
248 repaglinide) will be reduced to 50% of pre-admission dose to avoid risk of
249 hypoglycemia.
 - 250 • DPP4-inhibitors will not be used in combination with liraglutide during the study
251 period.
- 252

253 **Liraglutide Titration:**

254 Liraglutide will be administered once daily in accordance with a 3-4 week dose escalation

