6. Insulin administration (if needed).

Follow-up Care:

- If baseline visit was not fully completed at the time of discharge, patients will be scheduled to return for a short in-person visit to complete (body measurements) study procedures within 7 days of discharge. Research team will call to verify correct administration of study medication and availability of medications and glycemic control monitoring supplies.

- 300 • After discharge, a member of the diabetes research team will contact patients via
301 telephone call every 2 weeks for a total of 26 weeks.
- 302 • Patients will be asked to attend the next outpatient clinic visit at 4 weeks of hospital
303 discharge. During this visit, patients will receive 8 weeks drug supply of liraglutide and
304 will be asked to return to clinic at 12 weeks for the next outpatient visit. During this visit,
305 patients will receive 12 weeks (3 months) drug supply of liraglutide and will be asked to
306 return to a fourth and final visit at 26 weeks of hospital discharge.
- 307 • Recommendations on insulin adjustment will be provided to patients at each telephone
308 and clinic visits by a licensed physician (fellow or study physician) (see section Vf).

309 **During follow up we will collect the following information:**

- 310 1. Glycemic control:
- 311 a. Mean daily fasting and premeal blood glucose levels.
- 312 b. HbA1c at 3 and 6 months of discharge
- 313 c. Number of hypoglycemic events
- 314 - **Symptomatic hypoglycemia** is defined as an event with typical symptoms (i.e.,
315 sweating, palpitation, and feeling of hunger) with or without confirmation by
316 plasma glucose <70 mg/dl (3.9 mmol/L).
- 317 - **Severe hypoglycemia** is defined as episodes necessitating assistance and
318 associated with measured plasma glucose < 40 mg/dl (2.2 mmol/L) or with
319 prompt recovery after administration of carbohydrates, glucagon, or other
320 resuscitative actions. These episodes may be associated with sufficient
321 neuroglycopenia to induce seizure or coma. Blood glucose measurements may
322 not be available during such an event, but neurological recovery attributable to
323 the restoration of BG to normal is considered sufficient evidence that the event
324 was induced by low plasma glucose.
- 325
- 326 2. Diabetes treatment:
- 327 a. Number of patients receiving insulin therapy, dosage and compliance.
- 328 b. Use of liraglutide and other oral agents, dosage and compliance.

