Collect 7-point profile			x				x							x
Chemistry (BMP or CMP)							x							
Safety														
Adv events	x	x	x	x	x	x	x	x	x	x	x	x	x	x
Hypoglyc.	x	x	x	x	x	x	x	x	x	x	x	x	x	x
Trial material														
Drug dispense	x		x				x							
Drug account	x		x				x							x
Remind 7-point profile prior next visit		x				x							x	

549

- 550 ¹ TELEPHONE CALLS AND OUTPATIEN VISITS CAN BE COMPLETED ± 7 DAYS.
- 551 ² TO BE COMPLETED WITHIN 7 DAYS AFTER D/C (IF NOT COMPLETED AT TIME OF DISCHARGE)
- 552 ³ OBTAINED FROM MEDICAL RECORDS (HBA1C \leq 3MONTHS)
- 553

554 **STUDY DRUGS AND MATERIALS:**

555 Clinical trial materials will be labeled and should be handled and stored according to the
556 respective hospital's regulatory requirements. After discharge, patients will be re-started on their
557 pre-admission OADs (except for DPP4-inhibitors and selected drugs in the presence of
558 contraindication, i.e., metformin and renal failure). Liraglutide or glargine will be provided
559 during the study.

560

561 **Study medication(s) / devices(s)**

562 Liraglutide 6.0 mg/mL solution for s.c. injection, provided in 3 mL prefilled pen.

563

564 **Storage and Drug Accountability of Study Medication(s)**

565 Liraglutide will be stored and dispensed by the research pharmacy at each institution. The
566 liraglutide prefilled pen and glargine will be stored in a refrigerator at a temperature between
567 +2°C and +8°C (+36°F and +46°F).

568 Once dispensed and in use (after first opening), the liraglutide prefilled pen can be stored for one
569 month at room temperature (+15°C to +30°C)/(59°F to 86°F) or in a refrigerator (+2°C to
570 +8°C)/(+36°F to +46°F). The liraglutide prefilled pen must be protected from all sources of light
571 and the pen cap should be kept on when the pen is not in use.

572

573

574 **Drug accountability:** The trial product will be dispensed to each subject as required according
575 to treatment group. The research/clinical staff will perform drug accountability by asking
576 patients to return all unused, partly used and unused cartridges and vials of liraglutide and
577 glargine insulin at each visit.

578

579 **Randomization and Blinding**

580 This is an open label randomized controlled trial. Patients will be randomized consecutively
581 using a computer generated randomization table provided by [name] at the Emory
582 School of Public Health. Patient will be randomized (block randomization) based on glucose

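### Withdrawal criterion 2 lets an unblinded investigator take randomised patients out of the trial for judged non-compliance or late-found ineligibility, which can bias the week-26 non-inferiority comparison in either direction

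*Combined protocol and SAP*

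**What the plan says.** Withdrawal Criteria, item 2, opens "The subject may be withdrawn from the trial at the discretion of the investigator due to a" and continues "safety concern or if judged non-compliant with trial procedures or included in contravention", the last words referring to the inclusion and exclusion criteria. The exit is from the trial, the decision is discretionary, and no threshold or independent check on compliance is given. Under Randomization and Blinding the protocol states "This is an open label randomized controlled trial", so whoever decides knows the arm. Under Subject Replacement: "There will be no replacement of subjects in this trial".

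Compliance is also follow-up data. The Follow-up Care list includes "Use of liraglutide and other oral agents, dosage and compliance", and the flow chart schedules a compliance check at every contact after baseline. It also schedules a check of the withdrawal criteria at several contacts from week 2 to week 24.

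On the outcome, Study Outcomes says "The primary outcome of the study is to determine differences in HbA1c concentration at 26" weeks. Analysis of Primary Endpoint compares that value by t-test, Wilcoxon test or ANOVA, then by regression. The only wording on who is analysed is in Study Groups, repeated under Rationale for Study Population: "We plan to analyze a total of 280 patients (who receive study medication) with T2D at the time" of discharge. The documents define neither an all-randomised nor a per-protocol set. They give no method for a missing week-26 value and no provision for measuring HbA1c after withdrawal.

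**The concern.** Non-compliance and the discovery of an entry breach both come to light after randomisation. Neither requires data collection to stop. When an investigator who knows the arm can end a patient's participation on either ground, who contributes a week-26 HbA1c depends partly on a judgement made after assignment, and the two arms need no longer be comparable.

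The two grounds work differently. Removal for non-compliance takes out patients whose glycaemic control may be worse than average. Removal for ineligibility is a discretionary exclusion after randomisation; it does not in itself select compliers, but it can still depend on the arm.

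The primary claim is at stake because the margin is only 0.5% HbA1c, so a modest shift is a sizeable fraction of it. Several secondary outcomes are affected too: hypoglycaemic events, emergency visits and readmissions are no longer counted once the patient has left.

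**Working it through.** **The plan's own figure.** Sample Size and Power Calculations uses a margin of 0.5%, SD 1.5%, true difference 0, one-sided alpha 0.05 and 80% power, and gives 124 per group, raised to 140 for 10% attrition. The usual formula gives n = 2 × [1.5 × (1.645 + 0.842) / 0.5]² = 111.3, so 112 per group; the exact t calculation also gives 112. At 124 the power is 83.5%. The stated figure is therefore not reproduced, but the discrepancy errs towards a larger trial and does not bear on this point. With 140 randomised per arm and 10% lost, 140 × 0.9 = 126 remain and power is 84.0%; with 20% lost, 112 remain and power is 80.0%. Loss of numbers is not the main problem. Bias is.

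**Inputs for the bias.** From the plan: 126 per arm, SD 1.5%, margin 0.5%, one-sided alpha 0.05. Assumed, because the documents give no such figures:

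- share removed under item 2: 8-15% on liraglutide (fL) and 3-5% on glargine (fG);
- excess d in mean week-26 HbA1c of removed over kept patients: 0.5-1.5%, the same in both arms.

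**Shift.** In each arm the all-randomised mean equals the mean of those kept plus f × d. The difference observed in those kept therefore falls short of the all-randomised difference by

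shift = (fL − fG) × d.

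- Smallest: (0.08 − 0.05) × 0.5 = 0.015%.
- Largest: (0.15 − 0.03) × 1.5 = 0.18%.

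**Error at the margin.** SE = 1.5 × √(2/126) = 0.189. If the true all-randomised difference equals 0.5%, the chance of declaring non-inferiority is Φ(shift/SE − 1.645).

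| Shift towards liraglutide | Share of margin | Chance of false non-inferiority |
|---|---|---|
| 0 | 0% | 5.0% |
| 0.015 | 3% | 5.9% |
| 0.025 | 5% | 6.5% |
| 0.05 | 10% | 8.4% |
| 0.10 | 20% | 13.2% |
| 0.15 | 30% | 19.7% |
| 0.18 | 36% | 24.4% |

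**Zero and reversed cases.** With 10% removed in both arms and equal d, the shift is (0.10 − 0.10) × d = 0 and the error stays at 5%. If glargine loses more such patients, the sign changes. For a shift of −0.10 the error falls to Φ(−0.10/0.189 − 1.645) = 1.5%. Power at a true difference of 0 then falls from 84% to Φ((0.5 − 0.10)/0.189 − 1.645) = 68%, so a treatment that is in fact non-inferior is more likely to miss the claim.

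**The case against.** The strongest reply is that item 2 is permissive and excludes nobody from analysis. Planning to analyse 280 patients who receive study medication could be read as covering every treated patient. A reader might conversely infer that the protocol orders withdrawn patients to be left out of the analysis, and it does not. But a patient with no week-26 HbA1c cannot enter a t-test or regression on that value, and nothing says how the gap would be filled. The loss follows from item 2 together with those omissions.

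A second reply is that the wider cause lies elsewhere: items 1, 3, 4 and 5 also produce missing week-26 values, and item 4 is tied directly to glycaemia. That stands. Editing item 2 does not replace a missing-data method. It does remove the two grounds that are discretionary and need not end follow-up.

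A third concerns direction. A reader might infer that the rule makes non-inferiority easier to declare, because the Gastrointestinal side effects paragraph reports nausea and vomiting in up to "14% of patients receiving higher doses of liraglutide 1.8 mg in combination to metformin and" sulfonylurea. The comparator there is placebo plus oral agents (3.5%), not glargine. The plan also lets liraglutide escalation be extended for gastrointestinal events. Item 2 covers trial procedures generally, and glargine adjustment depends on patients' fasting readings, so non-compliance could be as common or more common on glargine. The liraglutide direction is plausible but not established.

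Finally, keeping non-compliers can pull the arms together, which is itself a hazard in a non-inferiority test. This is correct, and it is why both analyses are needed.

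**Conclusion.** The point holds as a weakness that can be cheaply mended. Followed as written, item 2 allows patients to leave the primary comparison on an unblinded, undefined judgement made after randomisation, and nothing elsewhere in the plan offsets this.

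The size rests wholly on assumed removal rates and an assumed excess HbA1c. Over the ranges used, the shift is 0.015-0.18% towards liraglutide and the one-sided error is about 6-24% instead of 5%. The upper part of that range is demanding: removals of 15% and 5% average 10%, which would use the plan's entire attrition allowance on this one criterion. Equal removal with equal excess gives no shift, and heavier removal on glargine reverses it. The documents support neither a fixed direction nor the reading that both grounds select compliers.

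**What to change.** In Withdrawal Criteria item 2, remove non-compliance and late-found ineligibility as grounds for leaving the trial. Record both as protocol deviations. Keep these patients in their assigned arm for the scheduled calls and the week-12 and week-26 HbA1c, subject to their own right to withdraw under item 1. Leave decisions on stopping study drug to the investigator, as now, but state that they are separate from leaving follow-up.

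In the statistical section, name the all-randomised comparison as primary. Require, rather than merely allow, a compliance-restricted analysis with a threshold fixed before analysis. Report removals by arm and reason.

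The cost is a short edit in each of two sections. The calls, visits and HbA1c tests already stand in the flow chart, though the documents show no budget against which to check the expense. Some non-compliant patients will still miss visits, so some week-26 values will remain missing. The primary estimate will also move towards the effect of assignment.
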